4.7 Safety – Bleeding

Bleeding events will be collected using the Bleeding Academic Research Consortium (BARC) bleeding definition. Additionally, the severity of bleeding will be categorized using the Global Utilization of Streptokinase and t-PA for Occluded Coronary Arteries (GUSTO) definition for severe, moderate, or mild bleeding. We will assess the effect of copayment reduction on bleeding using the same methods as the composite MACE outcome.

4.8 Unplanned Revascularization

We will assess the effect of copayment reduction on unplanned revascularization using the same methods as the composite MACE outcome.

4.9 Components of MACE

We will assess the effect of copayment reduction on each component of MACE using the same methods as the composite MACE outcome.

4.10 MACE plus unplanned revascularization

We will assess the effect of copayment reduction on the composite of all-cause death, recurrent MI, stroke, and unplanned revascularization using the same methods as the composite MACE outcome.

4.11 Cardiovascular Mortality

We will assess the effect of copayment reduction on cardiovascular mortality using the same methods as the composite MACE outcome.

4.12 As Treated Analysis

We will conduct an as treated analysis of the co-primary endpoints by excluding intervention patients who did not use the voucher during any of the 12 months of follow-up. We will use the same methods as described in Section 3.1 and 3.2, but we will re-fit the propensity score among this population. All tables included in Section 8.2.1 with the exception of Table 1 will be repeated for this subset of patients.

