2.2 Analysis Populations

The study population for primary and secondary analyses in ARTEMIS will start with all enrolled patients who survived the index MI hospitalization and did not withdraw from the study before hospital discharge. Since the intervention arm voucher provides copayment assistance for a generic (clopidogrel) or a brand (ticagrelor) P2Y₁₂ receptor inhibitor, we will conduct the primary endpoint analyses first among patients discharged on either clopidogrel or ticagrelor, and then repeat the analysis among all patients regardless of discharge P2Y₁₂ receptor inhibitor type.

2.3 Accounting for Hospital Clustering: Marginal vs. Conditional Modelling Approaches for Binary Endpoints

There are two general approaches that account for within hospital correlation in a statistical model; they are 1) marginal or population-averaged model and 2) conditional or subject-specific model. These two approaches differ in interpretation of model estimates and the way that correlation of measurements are incorporated in the model. For example, under the marginal model, the exponentiated treatment coefficient represents the odds of an average patient in the treatment group to be persistent compared to an average patient in the control group. Under the conditional random-effects model, the exponentiated treatment coefficient represents the odds of persistence for a treated person compared to the same person if they were not treated. As stated in the protocol we will use population averaged methods as our primary approach to account for hospital clustering.

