3.1 Non-persistence with antiplatelet therapy at 1 year

The co-primary endpoint of long-term non-persistence will be assessed using patient-reported medication non-persistence. Permanent and temporary discontinuation of a P2Y₁₂ receptor inhibitor will be queried at each follow-up interview. For patients with missing patient-reported medication information, pharmacy fill data will be used to ascertain persistence. Patients who have continued P2Y₁₂ receptor inhibitor use at one year from discharge with less than 30

Statistical Analysis Plan

continuous days of interruption will be considered persistent. We will use the last observation carried forward (LOCF) method for patients who died before one year or had missing 1 year P2Y₁₂ status.

The co-primary objective determines whether patient copayment reduction leads to higher long-term persistence with antiplatelet therapy at one year. The study endpoint for this objective is the proportion of patients at one year who had an interruption ≥ 30 days of P2Y₁₂ receptor inhibitor. The primary analysis will be a logistic regression model with parameters estimated using generalized estimating equations (GEE) to account for within hospital clustering and adjustment for selected patient characteristics (Section 8.3.1) which includes a propensity score for intervention (Section 8.3.2). The propensity score will be estimated using a logistic regression model for intervention group. Categorical variables will be included as sets of indicator variables. Continuous variables will be included assuming a simple linear relationship. Balance of covariates between intervention and usual care arms will be assessed using standardized differences as recommended by Austin [6]. We will assess functional form and possible transformations of the propensity score to be included in the outcome model. Cluster heterogeneity will be quantified using ICCs calculated from unadjusted and adjusted models. We will calculate the ICCs across all hospitals and also by treatment group.

After Steering Committee consensus, the randomization scheme was changed from 1:1 to 2:1 Usual Care vs. Intervention effective November 16, 2015. Randomization schema was added as a covariate for adjustment as shown in Section 8.3.1 and to the propensity model as shown in Section 8.3.2.

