3.2 MACE

The primary study objective evaluates whether patient copayment reduction leads to lower risk of MACE at one year. MACE is defined as the composite of all-cause death, recurrent myocardial infarction, and stroke. Follow-up will be censored at time of study withdrawal or last known alive. The time-to-first MACE event up to one year post-discharge will be compared between intervention and control arms. Cumulative incidence rates will be presented as Kaplan-Meier curves and in tables for 30 days, 6 months, and 1 year post-discharge. The primary analysis will be a Cox proportional hazards model accounting for within hospital clustering using robust standard errors and adjustment for selected patient characteristics (Section 8.3.1) which includes a propensity score for intervention. We will use the same propensity score described in section 3.1. Cluster heterogeneity will be quantified using ICCs calculated from unadjusted and adjusted models. We will calculate the ICCs across all hospitals and also by treatment group.

After Steering Committee consensus, the randomization scheme was changed from 1:1 to 2:1 Usual Care vs. Intervention effective November 16, 2015. Randomization schema was added as a covariate for adjustment as shown in Section 8.3.1 and to the propensity model as shown in Section 8.3.2.

4. Secondary Endpoints

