4.13 Exploratory Analysis

Reduction of the co-primary endpoint of MACE could be driven by several factors including improved adherence to therapy, increasing use of a higher-potency P2Y₁₂ receptor inhibitor, or both. Exploratory analyses will examine the associations of these two factors with MACE. In addition, instrumental variable analyses will be considered for the co-primary endpoints.

5. Subgroups

We will conduct subgroup analyses (Tables 3b, 4b, and 9b) for the following subgroups using the same methods as the primary analysis with the addition of the main effect for subgroup and an interaction term for subgroup by intervention. Indicator variables for the subgroups will be included in the propensity model for all subgroups except initial treatment selection.

- Age: Age ≥ 65 and age < 65
- Sex: Males and females
- Insurance status: private and non-private
- Race: White and non-White
- STEMI and NSTEMI
- In-hospital PCI and no in-hospital PCI

6. Secondary Analysis of Primary Endpoints

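### The as-treated analysis drops voucher non-users from the intervention arm only, so it selects partly on the persistence outcome and is likely to favour the intervention even if the voucher has no effect

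*SAP*

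**What the plan says.** Section 4.12 states: "We will conduct an as treated analysis of the co-primary endpoints", carried out "by excluding intervention patients who did not use the voucher during any of the 12 months of follow-up". I read this as never used in 12 months. Usual care has no voucher, so no matching exclusion applies there. The methods of Sections 3.1 and 3.2 are kept, "but we will re-fit the propensity score among this population". On reporting: "All tables included in Section 8.2.1 with the exception of Table 1 will be repeated for this subset of patients".

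Four other places bear on this.

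- **Section 2.2:** the voucher gives copayment help for clopidogrel or ticagrelor, so using it means filling one of those drugs.
- **Section 3.1:** "The study endpoint for this objective is the proportion of patients at one year who had an interruption ≥ 30 days" of a P2Y12 inhibitor. Last observation carried forward applies to patients who die before one year.
- **Section 3.2:** "The time-to-first MACE event up to one year post-discharge will be compared between intervention and control arms". The clock starts at discharge.
- **Section 4.13:** "In addition, instrumental variable analyses will be considered for the co-primary endpoints".

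The propensity covariates in Section 8.3.2 are baseline, in-hospital and site variables. Section 4.12 has no landmark, no time-varying exposure and no caveat on interpretation. Section 2.1 makes intention to treat the rule for all study objectives.

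**The concern.** The exclusion depends on behaviour after the start of follow-up and applies to one arm. An intervention patient who never fills, or who stops before first using the voucher, leaves the comparison. The equivalent usual-care patient stays in and counts as non-persistent. A patient who dies before first use also leaves one arm only.

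Re-fitting the propensity score balances measured characteristics known by discharge. Covariates such as insurance, financial hardship and missed doses may reduce the part due to who chooses to use the voucher. They cannot remove selection on later filling and survival.

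The analysis covers both co-primary endpoints, and the repeated shells (for example Tables 3a and 4a) carry effect estimates and p-values. A null intention-to-treat result could therefore sit beside a nominally significant as-treated benefit produced by the exclusion.

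**Working it through.** **Inputs from the SAP.** Section 1.4: control persistence 70%, target +4 points; control MACE 12%, target 9.84%; ICC 0.025 (persistence) and 0.01 (MACE); 300 sites, 36.67 patients per site, CV 0.65. Section 2: two-sided 0.05. Section 4.12 gives no figure of its own.

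**Benchmarks reproduced.** The continuity-corrected two-proportion formula gives 5392 and 4622 patients (persistence, 90% and 85% power) and 6728 and 7670 (MACE, 80% and 85%), all as stated. The persistence design effect is 1 + ((0.65² + 1) × 36.67 − 1) × 0.025 = 2.279, and 11,000 / 2.279 = 4827, as stated. For MACE, 1.512 gives 7277 against the stated 7278, which is rounding.

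**Assumptions.** No true effect, so 70% persistence and 12% MACE in both arms. Let u be the share of intervention patients who never use the voucher and g the gap in persistence between users and non-users. The SAP gives neither.

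**Persistence.** Since the arm average is 70%, users' persistence = 0.70 + u × g.

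| u | g | Users | Non-users | Apparent effect |
|---|---|---|---|---|
| 10% | 10 points | 71% | 61% | +1.0 |
| 20% | 20 points | 74% | 54% | +4.0 |
| 30% | 30 points | 79% | 49% | +9.0 |

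Check of the middle row: 0.8 × 74% + 0.2 × 54% = 70%.

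**Sign reversal.** If 20% are non-users and 80% of them persist, users = (0.70 − 0.2 × 0.80) / 0.8 = 67.5%, which is −2.5 points.

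**Chance of a false significant benefit in the middle row.** Under 1:1 allocation the effective sizes are 5500 / 2.279 = 2413 (usual care) and 4400 / 2.018 = 2180 (users, 29.33 per site). The null and alternative standard errors are 0.0133 and 0.0132, so z = (0.040 − 1.96 × 0.0133) / 0.0132 ≈ 1.06, about 85%. With u = 20% and non-user persistence of 60% (+2.5 points), the same calculation gives 46%. The 2:1 scheme changes these chances but not the bias.

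**The part that needs no difference in prognosis.** Suppose every patient would eventually use the voucher but must first be alive and on drug. Assume constant hazards, a mean time to first use of 15 to 60 days, and one-year mortality of 3% to 5%. The stopping hazard is −ln(0.70) = 0.357 per year.

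- At 15 days and 3% mortality, the use hazard is 365/15 = 24.33 and the death hazard 0.030. The share stopping first is 0.357 / 24.72 = 1.44%, and dying first 0.12%. Users' persistence is (0.70 − 0.0012 × 0.70) / 0.984 = 71.0%, or +1.0. Users' MACE is (0.12 − 0.0012 − 0.0144 × 0.12) / 0.984 = 11.9%, or 0.1 points lower.
- At 60 days and 5% mortality, 5.5% stop first, 0.8% die first and 0.15% have done none of these by one year. The same steps give persistence of about 74% (+4) and MACE of about 11.3% (0.7 points lower).

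These results agree with a simulation of 2,000,000 patients per scenario. Counting patients who die on drug as persistent, as Section 3.1 does, changes the persistence range only to about +1.0 to +3.9.

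**MACE if non-users are also at higher risk.** Users' rate = (0.12 − u × r) / (1 − u), with r the non-user rate. At u = 20% and r = 16% this is 11.0% (ratio 0.92). At u = 30% and r = 16% it is 10.3% (0.86). Reaching the design difference of 2.16 points needs r = 20.6% at u = 20%, or 17.0% at u = 30%.

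**The case against.** The strongest replies, and what stands of each:

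- **The direction is not fixed.** This stands. Every patient has a prescription drug benefit (Section 1.3) and one covered drug is generic, so a patient with a low copay can skip the voucher and still persist. In the repeat analysis of all discharge P2Y12 inhibitors (Section 2.2), patients on a drug outside the voucher are non-users however well they persist. A reader might infer that the bias always favours the intervention; the sign-reversal case shows that it need not.
- **Non-fatal events do not block later use.** This stands. A reader might treat every MACE before first use as an exclusion: removing 2% of patients that way gives (0.12 − 0.02) / 0.98 = 10.2%, a ratio of 0.85. But the rule removes only patients who never use the voucher, and a patient with a non-fatal infarction or stroke may use it afterwards. Essentially only death closes the window.
- **Early deaths do not inflate persistence.** This stands. Last observation carried forward counts a patient who dies on drug as persistent, so removing that patient slightly lowers intervention-arm persistence.
- **It is a labelled secondary analysis.** True, and it limits the consequence. It does not explain why the contrast should carry p-values in nearly every main table.
- **Section 4.13 already names instrumental-variable analyses.** It says only that they will be considered, and the method has its own weakness here: Sections 1.2 and 1.4 expect assignment to change discharge drug selection, which may act without voucher use.

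**Conclusion.** The point holds for the comparison as written: a one-sided exclusion after discharge, on behaviour closely tied to the persistence endpoint, with an adjustment that cannot remove it.

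For persistence the bias is likely to favour the intervention and can equal the 4-point design target. That it does equal the target cannot be claimed, because the non-use share and non-user outcomes are assumed. For MACE the built-in part is about 0.1 to 0.7 points under the stated hazards; anything larger needs non-users to be at higher risk, which the SAP neither states nor excludes.

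The primary intention-to-treat results are untouched. This should be changed, but it does not threaten the main conclusions.

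**What to change.** 1. **Section 4.12:** label the voucher-user tables descriptive, and remove between-arm p-values and effect claims from them. State that never having used the voucher is the meaning of the exclusion, if that is intended.
2. **Section 4.13:** replace the wording that instrumental-variable analyses will be considered with a commitment to a complier-average analysis of both co-primary endpoints, with site assignment as the instrument. As vouchers exist in one arm only, the estimate is the intention-to-treat difference in one-year risk divided by the proportion of intervention patients who used the voucher. Account for randomization scheme (1:1 and 2:1) and the randomization strata, and use hospital-clustered or hospital-bootstrap intervals. With no true effect it targets 0 / (1 − u) = 0 whatever the non-use share.
3. **State its assumption:** assignment acts only through voucher use. Say that this may fail because assignment may also change drug selection at discharge (Sections 1.2 and 1.4).

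The cost is SAP wording and one added analysis. The downsides are that assumption and wider intervals: with 20% non-use, roughly 1 / 0.8 = 1.25 times the width of the intention-to-treat interval.

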4.13 Exploratory Analysis

Reduction of the co-primary endpoint of MACE could be driven by several factors including improved adherence to therapy, increasing use of a higher-potency P2Y₁₂ receptor inhibitor, or both. Exploratory analyses will examine the associations of these two factors with MACE. In addition, instrumental variable analyses will be considered for the co-primary endpoints.

5. Subgroups

We will conduct subgroup analyses (Tables 3b, 4b, and 9b) for the following subgroups using the same methods as the primary analysis with the addition of the main effect for subgroup and an interaction term for subgroup by intervention. Indicator variables for the subgroups will be included in the propensity model for all subgroups except initial treatment selection.

- Age: Age ≥ 65 and age < 65
- Sex: Males and females
- Insurance status: private and non-private
- Race: White and non-White
- STEMI and NSTEMI
- In-hospital PCI and no in-hospital PCI

6. Secondary Analysis of Primary Endpoints

6.1 Non-persistence with antiplatelet therapy at 1 year

Propensity matched analysis: Within each of the four randomization strata defined, using medians across potential sites from survey conducted prior to ARTEMIS, by high (≥ 400) vs. low (< 400) annual site AMI volume and high ($\geq 15\%$) vs. low ($< 15\%$) proportion of ticagrelor use and by randomization scheme (2:1 vs. 1:1), we will match intervention arm patients to usual care patients. Matching within randomization scheme and strata forces matches across sites of similar size and proportion ticagrelor use and time of site randomization. To run the computerized

Statistical Analysis Plan

matching of intervention to usual care patients, we will utilize the gmatch macro publicly available from the Mayo Clinic Division of Biomedical Statistics and Informatics website of locally written SAS macros. This macro was downloaded on 5/13/13 from the following website: <http://mayoresearch.mayo.edu/mayo/research/biostat/sasmacros.cfm>. The gmatch macro performs greedy matching of cases to controls (intervention patients to usual care patients) within a pre-specified caliper. Greedy matching starts by creating two pools of patients; 1 pool for intervention patients and 1 pool for usual care. Each pool is randomly sorted, then for each intervention patient, we select the first usual care patient in the randomly sorted pool that has a propensity score within the pre-specified caliper. Once a match is made, it is never broken even if another closer match exists. Patients will be matched based on the propensity for intervention group using the propensity score estimated in the primary analysis. If there are no usual care patients with a propensity score within the caliper of a given intervention patient then that intervention patient is not included in the matched sample. We will match on the logit of the propensity score and use a caliper with a width of 0.2 times the standard deviation of the logit of the propensity score as suggested by Austin [7]. To estimate the intervention effect on non-persistence among the propensity matched sample we will fit a logistic regression model stratified by matched pair. Matching on the propensity score is expected to reduce most of the observed differences in patient case mix between the two groups so further adjustment is not necessary.

Random Intercepts for Hospital: We will fit a logistic regression model with adjustment for the same selected patient characteristics and same propensity score as in the primary analysis. The only modification is that we will account for within hospital clustering using random intercepts for hospitals instead of GEE.

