6.2 MACE

Propensity matched analysis: We will use the same matched sample described in section 6.1 to estimate the intervention effect on MACE using a Cox proportional hazards model stratified by matched pair.

Random Intercepts for Hospital: We will fit a Cox proportional hazards model with adjustment for the same selected patient characteristics and same propensity score as in the primary analysis. The only modification is that we will account for within hospital clustering using random intercepts for hospitals instead of robust standard errors.

7. References

2. Eldridge, S.M., D. Ashby, and S. Kerry, *Sample size for cluster randomized trials: effect of coefficient of variation of cluster size and analysis method*. Int J Epidemiol, 2006. **35**(5): p. 1292-300.
4. Ho, P.M., et al., *Multifaceted intervention to improve medication adherence and secondary prevention measures after acute coronary syndrome hospital discharge: a randomized clinical trial*. JAMA Intern Med, 2014. **174**(2): p. 186-93.
6. Austin, P.C., *Balance diagnostics for comparing the distribution of baseline covariates between treatments groups in propensity-score matched samples*. Statistics in Medicine, 2009. 28: p. 3083-3107.
7. Austin, P.C., *Some methods of propensity-score matching had superior performance to others: results of an empirical investigation and Monte Carlo simulations*. Biometrical Journal, 2009. 51: p. 171-184.

8. Appendices

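### The secondary matched analyses take the first usual-care patient inside the caliper rather than the closest, leaving a small, one-directional and cheaply avoidable residual imbalance

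*SAP*

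**What the plan says.** SAP section 6.1 plans a propensity-matched analysis of non-persistence as a secondary analysis of a co-primary endpoint. Matching is 1:1 and greedy, within the four site strata and the two randomization schemes, so within eight cells. Three elements matter here.

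- **Selection.** Both pools are put in random order. For each intervention patient, "we select the first usual care patient in the randomly sorted pool that has a propensity score within the pre-specified caliper". The next sentence adds: "Once a match is made, it is never broken even if another closer match exists".
- **Caliper.** Matching is on the logit of the score, with a "caliper with a width of 0.2 times the standard deviation of the logit of the propensity score". The SAP does not say whether this SD is taken over all patients or within a matching cell.
- **Model.** For the effect, "we will fit a logistic regression model stratified by matched pair". Matching is "expected to reduce most of the observed differences in patient case mix between the two groups so further adjustment is not necessary".

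Section 6.2 carries the sample over to the other co-primary endpoint: "We will use the same matched sample described in section 6.1 to estimate the intervention effect on MACE", with a pair-stratified Cox model.

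Section 3.1 plans standardized differences to assess balance between arms in connection with the propensity score. It sets no threshold and does not expressly call for the check to be repeated in the matched sample.

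**The concern.** Under this rule a usual-care patient 0.19 SD away is taken ahead of one 0.01 SD away if he or she comes earlier in the sort. If such misses fell evenly on both sides they would average out over pairs, but they do not. The usual-care list is sorted once, worked through in order, and its members are not reused. Intervention patients have higher scores on average, so at higher scores there are more of them per usual-care patient, and the early entries there are used up sooner. The first entry still free inside the caliper therefore lies below the intervention patient's score more often than above it.

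What is at stake is the value of these analyses as a check. They test, by a different route from the regression models, whether case-mix differences between unblinded hospitals explain the co-primary results. A check that retains part of the measured imbalance, always in the same direction, is weaker than the same data allow. With no covariates in the matched models, nothing later removes that part.

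**Working it through.** The SAP states no figure for residual imbalance, so there is none to reproduce. The two selection rules were compared by simulation.

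**Inputs from the SAP.** About 11,000 patients (section 1); eight matching cells, caliper 0.2 SD of the logit score, greedy matching in random order (6.1); 1:1 and later 2:1 usual care to intervention (2); scheme included in the propensity model (8.3.2).

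**Assumptions, because the SAP does not give them.** The separation of the arms, d (difference in mean logit score divided by its within-arm SD), was varied from 0.1 to 1.5 with normal scores. The share of patients under 2:1 was varied from 20 to 50%.

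**Measure.** Residual % = mean within-pair difference in logit score ÷ difference in means before matching × 100.

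Selected results (eight-cell rows have a quarter of patients under 2:1):

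| Setting | d | First: % left | First: SD left | Closest: % left | Intervention patients matched, first → closest |
|---|---|---|---|---|---|
| One pool, 1000 vs 2000 | 0.2 | 21.5 | 0.041 | 0.2 | 99.8% → 99.7% |
| | 0.5 | 16.3 | 0.080 | 0.3 | 98.2% → 97.3% |
| | 1.0 | 12.3 | 0.124 | 0.8 | 85.6% → 80.7% |
| | 1.5 | 10.5 | 0.158 | 1.1 | 67.0% → 62.7% |
| Eight cells, within-cell SD | 0.25 | 17.6 | 0.042 | 1.1 | 93.8% → 91.4% |
| | 0.5 | 14.0 | 0.070 | 1.0 | 86.0% → 83.5% |
| | 1.0 | 10.7 | 0.108 | 1.2 | 69.3% → 65.7% |
| Eight cells, overall SD | 0.25 | 39.0 | 0.096 | 2.1 | 95.9% → 91.7% |
| | 0.5 | 18.7 | 0.093 | 1.3 | 87.3% → 83.7% |
| | 1.0 | 11.7 | 0.117 | 1.2 | 69.8% → 65.6% |

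Over all settings, first-in-caliper left about 10 to 30%, with the 39% case on top. Smaller pools (600 vs 600 and 450 vs 900, d from 0.1 to 1.0) gave 9.5 to 14%, against 0 to 1.3% for the closest. In absolute terms the residual ran from about 0.01 SD (d = 0.1) to about 0.17 SD (d = 1.5, equal pools: 11.1% × 1.5 = 0.167).

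**Why the choice of SD matters.** Scheme is in the score, so moving from 1:1 to 2:1 shifts the logit by ln 2 = 0.693. With a quarter of patients under 2:1 this adds 0.25 × 0.75 × 0.693² = 0.090 to the overall variance. In the model used, the within-arm SD of the logit equals d. At d = 0.25 the overall SD is therefore about √(0.0625 + 0.090 + 0.001) = 0.39, where 0.001 is the between-arm part. The caliper is 0.2 × 0.39 = 0.078, or 0.31 within-arm SDs instead of about 0.2.

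**Effect on the estimate.** If measured confounding alone would give an odds ratio C, and it falls in proportion to the logit-score difference, a share f left over gives exp(f × ln C).

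- C = 1.10: f = 0.10 gives exp(0.10 × 0.0953) = 1.010; f = 0.18 gives 1.017; f = 0.30 gives 1.029.
- C = 1.30: f = 0.10 gives 1.027; f = 0.18 gives 1.048.

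The planned effects, for comparison: OR for non-persistence (0.26/0.74) ÷ (0.30/0.70) = 0.82; HR for MACE ln(1 − 0.0984) ÷ ln(1 − 0.12) = 0.81.

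**The case against.** The best defence is that the SAP promises only to remove most of the observed differences. In most settings the rule does so: removing 82 to 90% is most. Nothing in the SAP is contradicted or miscalculated, and this stands. The case for change is only that the same caliper and data can remove about 98% or more.

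Second, no primary conclusion rests on these analyses. The primary models in 3.1 and 3.2 adjust for the propensity score and the covariates in 8.3.1, and the random-intercept analyses in 6.1 and 6.2 keep that adjustment. None of them uses the matched sample. This stands too. A reader might infer that the co-primary results are biased; the document does not support that.

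Third, the effect is small against sampling error. A trial-like simulation with ten prognostic covariates, each differing by 0.10 SD, moved the null log OR by about 0.022 between the two rules (OR 1.02). It assumed 180 sites at 1:1 and 120 at 2:1, so 180/2 + 120/3 = 130 intervention sites. That gives 130 × 36.67 × 0.875 ≈ 4,170 pairs. At 30% non-persistence, 2 × 0.3 × 0.7 = 42% of pairs are discordant, about 1,752, so the standard error is 2/√1752 = 0.048 before clustering. The shift is under half of that. It also presupposes sizeable confounding: covariate residuals of 18% and 2% imply 0.022 ÷ 0.16 ≈ 0.14 on the log scale, an OR of about 1.15. MACE was not simulated.

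Finally, the sentence about never breaking a match describes greedy matching in general. The replacement rule below is greedy as well, so the weakness lies in how a control is chosen inside the caliper.

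**Conclusion.** The point holds as a modest weakness of the secondary matched analyses. Section 6.1 is explicit about taking the first eligible usual-care patient, 6.2 inherits the sample, and the matched models contain no covariates. The comparison between rules came out the same way in every setting tried: about 10 to 30% of the logit-score difference left (up to about 39%), against about 0 to 2% with the closest control.

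The exact percentage should not be read as a property of this trial. It depends on a separation between arms that the SAP does not state, on the SD that sets the caliper, and on pool size. In percentage terms it is largest where the arms differ least, which is also where there is least measured confounding to leave behind. The likely shift, an OR of about 1.01 to 1.02 where measured confounding alone would give 1.10, rests on residual shares of 10 to 18% and on confounding that scales with the logit score. It is small beside planned effects of 0.82 and 0.81. This is a cheap improvement of low priority.

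**What to change.** In section 6.1, replace the selection rule with this: for each intervention patient, taken in random order with a fixed seed, select the unused usual-care patient in the same randomization scheme and stratum who has the smallest absolute difference in the logit of the propensity score, provided that difference lies within the 0.2 SD caliper. Use the resulting sample in 6.2. The same sentence should say which SD, overall or within cell, sets the caliper.

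The cost is somewhat fewer matched intervention patients: mostly 0 to 4 percentage points in these runs, and about 5 at the most. A fall from 85% to 81% widens intervals by about √(85/81) − 1 = 2%. The matching step also has to change. Whether the named macro offers closest-match selection as an option or has to be replaced cannot be judged from the SAP.
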